### **Hypothesis:**

H0:  $\mu_1 = \mu_2$  where  $\mu_1$ = mean change in CRIS subscale from time 1 to time 2 in self-management group and  $\mu_2$ = mean change in CRIS subscale from time 1 to time 2 in supported discharge group  
H1:  $\mu_1 \neq \mu_2$

**Power Calculation:** PASS (Power Analysis and Sample Size Software, Kaysville, UT, 2008) was used for the power calculation. The primary outcome of this study is the frequency of social interactions measured via the Extent of Participation subscale of the CRIS. The power calculation was performed based on the hypothesis listed above by using a two-sided t-test with assumption of normality. The level of significance was set at 0.05 and power was set at 90%. The effect size and standard deviation used for the power calculation were estimated based on a previous VA study and clinical judgment. 44 subjects in each

[figure not shown]
group, for a total of 88 subjects will provide 90% power to test an effect size of 0.71 with a SD of 7 for difference in CRIS subscale score between groups with  $\alpha=0.05$  (two sided). After adjustment for 20% loss to follow-up, we will recruit 55 subjects in each group of this study, a total of 110 subjects.

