### **Hypothesis 1: Outcome Variables Main Effects for Community Re-integration Factors**

This algorithm is based on the assumption that an interaction between the intervention group and control groups can be modeled as a fixed effect. An LMM will then be used to evaluate whether the intervention had an effect at any time point or whether the intervention influenced change (growth, trajectory) in the outcome over the course of the study. The following will be considered for the analytical strategy:

- ANOVA, Repeated-measures ANOVA as well as MANCOVA will be used to compare the effect of the COMPASSgoal intervention vs. supported discharge group determined via baseline assessment. ANOVA will be used to compare the change from pre- to post-intervention between the two groups. Furthermore, in order to analyze the main effect of the COMPASSgoal intervention over time, a two-way repeated measures parametric ANOVA, as well as a non-parametric repeated measures Friedman ANOVA, will be performed, using the baseline time point, levels of TBI self-efficacy, or real-world tasks performance as the dependent variables. The levels of the repeated measures factor correspond to the number of assessments: baseline (pre-intervention) and 2 months post-intervention. The between-groups factor will be the intervention group vs. the supported discharge group. MANCOVA analysis will focus on the contrast in TBI self-efficacy between the intervention and supported discharge groups while accounting for a specified covariate: level of executive impairment as defined by FrSBE. In the case of non-normal residuals, we will use a nonparametric repeated measures approach. In the case of missing data, an LMM, which uses a maximum likelihood estimate to correct for unequal number of measures per subject, will be employed.
- *We will use Linear mixed models to control for potential confounding variables and baseline values will be utilized as a covariate. These models will allow for the additional control of potential within subjects clusters. These clusters, though not part of the formal hypothesis testing but byproducts of these models, will allow for conceptualization of additional future hypotheses.*

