### **Hypothesis 2: Psychosocial Profile as Mediator of the Responsiveness to the Intervention Over Time Course**

To explore Hypothesis 2, we will utilize a multistage analytic strategy. Because of the possibility of missing data due to non-responses, missed visits, attrition, and mortality over the course of the study, the statistical analysis presents certain challenges. At the first stage, a linear mixed model will be used to incorporate all available data, evaluate trends, and estimate change of outcome variables without discarding cases that have missing data points. Furthermore, linear mixed models (LMM) control for confounding effects of other repeatedly measured covariates while accounting for the correlation among repeatedly measured outcomes. SAS PROC MIXED will be used to estimate a LMM for each outcome of interest. For categorical outcomes, generalized estimating equations (GEEs) will be used to evaluate trends over time while accounting for the dependency among the repeatedly measured outcomes. GEEs will be solved using SAS PROC GENMOD.

Also for **Hypothesis 2** analysis the following will be considered:

- Linear mixed models (LMM) will be used to control for confounding effects of other repeatedly measured covariates while accounting for the dependency among the repeated measured outcomes and covariance matrix.
- We will construct a model which only includes the repeated measures variables to obtain means, variances, and covariances.
- We will add time-invariant variables such as treatment group into the multi-level model (MEME) to predict the change over time in executive dysfunction and associated real-life task performance. Therefore, this method will allow us to address individual growth, identify latent trajectories of growth, relate the observed changes to pre-existing differences between TBI subjects, and determine treatment effects.

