Then, we will use linear growth curves to assess individual differences as well as group differences by following a two-stage LGM. At the second stage, we will construct a model that only includes the repeated measures variables to obtain means, variances, and covariances. At stage three, we will add time-invariant variables such as age, gender, and education into the model to predict change over time in executive function and real-world performance. We will also be able to refine our model at any level by assessing the fit after additional variables are inserted. The obtained covariance structure will allow us to draw inferences with regards to linear increases or decreases in executive dysfunction and real-world performance over time. Therefore, this method will allow us to address individual growth, identify latent trajectories of growth, and finally, relate the observed changes to pre-existing differences between TBI subjects.

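### The Hypothesis 1 mixed model is described as maximum likelihood with no small-sample degrees of freedom; fitted that way, its between-arm standard errors are slightly too small (minor)

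*Combined protocol and SAP*

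**What the plan says.** In the Statistical Analysis Plan, the Hypothesis 1 section states that, when data are missing, "an LMM, which uses a maximum likelihood estimate to correct for unequal number of measures per subject, will be employed". The same section also gives mixed models two wider roles. One is to assess the intervention at each visit and over the trajectory. The other is to adjust for confounders, which are not named, with the baseline value as a covariate. FrSBe appears in that section as the covariate of the MANCOVA, not of the mixed model.

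No section names REML, a degrees-of-freedom method or a reference distribution. The general software is SPSS (Data Collections and Storage). The Hypothesis 2 section says that "SAS PROC MIXED will be used to estimate a LMM for each outcome of interest", with no estimation option, and that "We will also be able to refine our model at any level by assessing the fit after additional variables are inserted".

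The sample size rests on a different test. It was obtained "by using a two-sided t-test with assumption of normality" of the change from time 1 to time 2, and "The level of significance was set at 0.05 and power was set at 90"%. The Overview and the Hypothesis 1 section assign that pre-to-post comparison to ANOVA.

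**The concern.** ML estimates the variance as if the fixed effects were known. Its variance estimate is too small by a factor of about (N − p)/N, where p is the number of between-subject fixed effects. At the planned size this is small but not zero, and it grows with each covariate added. It makes intervals too narrow and p-values too small, so it always favours declaring a difference between arms.

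The mixed model is not a remote fallback. The plan allows for 20% loss to follow-up, rules out imputing missing outcomes, and also uses the model for effects by visit and for covariate adjustment. A reader of the SAP cannot tell which estimator and which reference distribution would produce the reported p-values.

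**Working it through.** **Inputs from the plan.** Two-sided α 0.05; power 90%; standardized effect 0.71 with SD 7 (0.71 × 7 = 4.97 points); 44 evaluable per arm, so N = 88; 20% loss; 55 per arm randomized, 110 in total.

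**Plan's own figure.** Normal approximation: n = 2(1.960 + 1.282)²/0.71² = 21.02/0.5041 = 41.7, so 42 per arm. The noncentral t gives 43 per arm for 90% power, and 90.9% power at 44. Inflation: 44/0.80 = 55 per arm, 110 in total. The stated size is reproduced, so N = 88 is the right evaluable number.

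**Inputs not in the plan (assumed).** The number of fixed effects p, the reference distribution, and the within-person correlation in the simulations.

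**Formula.** For a between-subject contrast, the ratio of ML to REML standard error is r = √((N − p)/N). The type I error under ML is 2·P(T with N − p df > c·r), where c is 1.96 (normal) or the t quantile.

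Example, p = 4: r = √(84/88) = 0.977, a shortfall of 2.3%. Normal reference: c·r = 1.96 × 0.977 = 1.915, giving 5.9%. t reference: 1.989 × 0.977 = 1.943, giving 5.5%.

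| p (N = 88) | SE shortfall | ML, normal | ML, t | REML, normal |
|---|---|---|---|---|
| 2 | 1.1% | 5.6% | 5.3% | 5.3% |
| 3 (intercept, arm, baseline) | 1.7% | 5.7% | 5.4% | 5.3% |
| 4 (one more, e.g. FrSBe) | 2.3% | 5.9% | 5.5% | 5.3% |
| 7 | 4.1% | 6.4% | 6.0% | 5.3% |
| 10 | 5.9% | 6.9% | 6.5% | 5.4% |

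In this formula REML with a t reference is exact at 5.0%. The last column shows how much comes from a normal cutoff alone. At p = 3, ML adds 5.7 − 5.3 = 0.4 points; at p = 10 it adds 6.9 − 5.4 = 1.5 points.

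**Simulation 1.** Random-intercept model under no effect, 110 randomized, about 20% monotone dropout, correlation 0.5, 3,000 runs per design (Monte Carlo SE about 0.4 points).

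- *Arm effect, baseline as the only covariate:* SE 1.4-1.6% small; ML error 5.9-6.1% (normal) or 5.6-5.8% (t).
- *Three extra covariates:* SE 3.2% small; 6.5% or 6.1%.
- *Seven extra covariates:* SE 5.4% small; 6.3% or 6.0%.
- *Group-by-time contrast, baseline as one of the outcomes:* SE 1.0-1.1% small with 0 or 5 subject-level covariates. With a normal cutoff, ML exceeds REML by only 0.1-0.3 points (5.2% against 5.0%, 6.2% against 6.1%, 5.9% against 5.6%).
- *REML with a t reference, all seven designs:* 4.7-5.5%.

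**Simulation 2.** Two follow-up visits, unstructured covariance, correlation 0.7, 20% without T2 and 25% without T3, 10,000 runs each. With 2, 6 or 10 baseline covariates (p = 4, 8 or 12 at T2), the mean ML and REML standard errors are 0.2107/0.2153, 0.2104/0.2195 and 0.2107/0.2248, so ML is 2.1%, 4.1% and 6.3% short. ML error is 6.0%, 6.7% and 7.3% (normal) or 5.8%, 6.2% and 6.8% (t). REML with t gives 5.4%, 5.2% and 5.1%. The last case, with 12 fixed effects, lies beyond anything the plan suggests.

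The formula and both simulations agree on direction and order of size.

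**The case against.** The strongest reply is that the plan never chose full ML. The clause explains why a mixed model copes with unequal numbers of visits; REML is also likelihood-based and shares that property. If the analyst uses a REML setting, the bias does not arise. This is fair, and it is why the size is stated as conditional. Read literally, though, the text names ML, and nothing elsewhere corrects it.

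Three stronger readings are tempting and are not supported:

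- *The 5% level behind the sample size is lost.* That level belongs to a t-test on pre-to-post change, which the SAP gives to ANOVA, and ANOVA has no ML variance bias. The Missing Data section also makes complete-case analysis the usual course if data are judged missing completely at random.
- *The trial has a 6-7% false-positive rate.* That needs about 7-10 fixed effects, and at the upper end mostly a normal cutoff. The plan states neither. The only covariate it names for the mixed model is baseline.
- *The Hypothesis 2 models share the fault.* That section states no estimator, and refining a model by its fit does not imply that final inference is by ML.

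The point that the change contrast barely suffers also stands, but only when baseline is modelled as an outcome. Where baseline is a covariate, as the Hypothesis 1 section also plans, the arm effect is a between-subject contrast and each added covariate enlarges the shortfall.

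**Conclusion.** The point holds as a minor one. If full ML is fitted as written to about 88 evaluable Veterans with baseline as a covariate, between-arm standard errors are about 1.5-2.5% too small and type I error is about 5.4-5.9%. A 95% interval would then cover about 94.1-94.6% of the time. With 7-10 fixed effects the shortfall is about 4-6% and type I error about 6.0-6.9%; the lower figure goes with 7 effects and a t reference, the upper with 10 and a normal reference. These figures assume that maximum likelihood means full ML. They include a part, about 0.3-0.4 points, that a normal cutoff causes even under REML. The effect is one-sided in its consequence and easily avoided, but it does not undermine the powered comparison.

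**What to change.** In the Hypothesis 1 section, replace the reference to maximum likelihood with: *restricted maximum likelihood, with small-sample (e.g. Kenward-Roger or Satterthwaite) degrees of freedom, for all final tests and confidence intervals*. Add that ML is used only to compare models with different fixed effects. State in the same place which package fits this model, since SPSS is named generally and PROC MIXED only under Hypothesis 2, and confirm that it offers the chosen degrees-of-freedom method. Listing the confounders in advance would also fix p. Stating the estimator for the Hypothesis 2 models would remove doubt there, but that is a clarification and not a correction.

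The cost is a sentence or two of SAP text and slightly wider intervals. No design, data collection or sample-size change is needed.

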### **Hypothesis 2: Psychosocial Profile as Mediator of the Responsiveness to the Intervention Over Time Course**

To explore Hypothesis 2, we will utilize a multistage analytic strategy. Because of the possibility of missing data due to non-responses, missed visits, attrition, and mortality over the course of the study, the statistical analysis presents certain challenges. At the first stage, a linear mixed model will be used to incorporate all available data, evaluate trends, and estimate change of outcome variables without discarding cases that have missing data points. Furthermore, linear mixed models (LMM) control for confounding effects of other repeatedly measured covariates while accounting for the correlation among repeatedly measured outcomes. SAS PROC MIXED will be used to estimate a LMM for each outcome of interest. For categorical outcomes, generalized estimating equations (GEEs) will be used to evaluate trends over time while accounting for the dependency among the repeatedly measured outcomes. GEEs will be solved using SAS PROC GENMOD.

Also for **Hypothesis 2** analysis the following will be considered:

- Linear mixed models (LMM) will be used to control for confounding effects of other repeatedly measured covariates while accounting for the dependency among the repeated measured outcomes and covariance matrix.
- We will construct a model which only includes the repeated measures variables to obtain means, variances, and covariances.
- We will add time-invariant variables such as treatment group into the multi-level model (MEME) to predict the change over time in executive dysfunction and associated real-life task performance. Therefore, this method will allow us to address individual growth, identify latent trajectories of growth, relate the observed changes to pre-existing differences between TBI subjects, and determine treatment effects.

Then, we will use linear growth curves to assess individual differences as well as group differences by following a two-stage LGM. At the second stage, we will construct a model that only includes the repeated measures variables to obtain means, variances, and covariances. At stage three, we will add time-invariant variables such as age, gender, and education into the model to predict change over time in executive function and real-world performance. We will also be able to refine our model at any level by assessing the fit after additional variables are inserted. The obtained covariance structure will allow us to draw inferences with regards to linear increases or decreases in executive dysfunction and real-world performance over time. Therefore, this method will allow us to address individual growth, identify latent trajectories of growth, and finally, relate the observed changes to pre-existing differences between TBI subjects.

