### Study Hypotheses:

[figure not shown]
Study Hypothesis 1: Participants in the COMPASSgoal group will have higher TBI self-efficacy and higher community integration scores over time than participants in the supported discharge group matched on executive dysfunction score;

Study Hypothesis 2: *Individual psychosocial profile (emotional status, resilience, and level of post-traumatic stress disorder, PTSD) will mediate the responsiveness to the COMPASSgoal intervention, measured through the standardized experimental performance of everyday tasks, in Veterans with impaired executive function due to TBI.*

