## STATISTICAL ANALYSIS PLAN

### Overview

For this project, we plan to collect three major types of data assessed at times 1-3 (baseline/pre-intervention, 2 months/post-intervention, and 3 months follow up): community integration parameters including educational attainment and employment, individual characteristics such as PTSD; TBI self-efficacy, emotional status, coping, performance of real-world tasks, resilience and life satisfaction, and neuropsychological parameters including overall cognitive and executive functioning. Though we have removed the physical function assessments from future data collection, previously collected data on physical function may still be used for data analysis and subsequent publication and presentation purposes. The primary outcome will be the change in the three major types of parameters from pre- to post-intervention. Depending upon the hypothesis being tested (see Specific Aims section), participants will be stratified according to level of executive functioning, severity of conditions secondary to TBI (PTSD, level of functioning, emotional status), or degree of societal participation. Dependent variables will include TBI-self-efficacy, community integration indices, educational or work attainment as defined by the ICF qualifiers, and life satisfaction. Both objective (e.g. executive performance) and subjective (e.g., perceived TBI self-efficacy) data will then be obtained based on repeated measures over the three-year period. Multiple regression models will be fitted to explore continuous primary and secondary outcomes differentiating between groups at each time point and changes at the intra-individual and inter-individual levels over time. For categorical outcomes (e.g., low/high executive performance, or work status such as unemployed/employed, part-time/full-time), unconditional logistic and/or multinomial regression models will be implemented.

The basic testing of the hypotheses will involve ANOVA test and repeated measures ANOVA test. Bonferroni adjustments will be made to account for multiple testing.

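### Hypothesis 2 is stated as mediation by psychosocial profile, but no analysis in the SAP specifies a mediation test or an arm-by-profile interaction, so the plan as written does not test it

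*Combined protocol and SAP*

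**What the plan says.** The Study Hypotheses section states: "Individual psychosocial profile (emotional status, resilience, and level of post-traumatic stress disorder, PTSD) will mediate the responsiveness to the" intervention, with response measured by performance of everyday tasks. The SAP heading for Hypothesis 2 repeats the mediator role, and Overall Study Design says that the study will test both hypotheses.

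The SAP material bearing on Hypothesis 2 is as follows.

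- **Overview, stratification:** "Depending upon the hypothesis being tested (see Specific Aims section), participants will be stratified according to level of executive functioning", or by "severity of conditions secondary to TBI (PTSD, level of functioning, emotional status", or by degree of societal participation.
- **Overview, tests:** "The basic testing of the hypotheses will involve ANOVA test and repeated measures ANOVA test", with Bonferroni adjustment for multiple testing.
- **Hypothesis 2, opening:** "To explore Hypothesis 2, we will utilize a multistage analytic strategy". Mixed models (GEE for categorical outcomes) estimate trends.
- **Hypothesis 2, covariates:** "Linear mixed models (LMM) will be used to control for confounding effects of other repeatedly measured covariates".
- **Hypothesis 2, multilevel model:** "We will add time-invariant variables such as treatment group into the multi-level model (MEME) to predict the change over time in executive dysfunction" and related task performance.
- **Hypothesis 2, growth model, third stage:** "we will add time-invariant variables such as age, gender, and education into the model to predict change over time in executive function" and real-world performance. Further unnamed variables may be added and judged by fit.

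**The concern.** A mediation hypothesis makes a claim about a path: the intervention changes the psychosocial measure, and that change carries some of the effect on the outcome. A moderation hypothesis makes a different claim: the effect differs by the participant's starting profile. Each needs its own term in the model, and the SAP writes down neither.

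The analyst would have to choose after seeing the data: mediation or moderation, which scores, baseline or later values, strata or continuous scores, which cut-points and which outcome. A result reached that way could not be presented as a pre-specified test of one of the study's two hypotheses.

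The confounder wording adds a second risk. If post-randomisation PTSD or distress scores enter as covariates, the treatment coefficient stops being the total effect, and the part removed is the part that Hypothesis 2 asks about.

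**Working it through.** **1. The plan's own figure.** The sample size is for the CRIS change only. Inputs from Power and sample size calculation: standardised effect 0.71, two-sided 0.05, 44 per group. The standard error is sqrt(2/44) = 0.213 SD, so the noncentrality is 0.71/0.213 = 3.33 on 86 df, and power is 0.909. Exactly 90% power needs 42.7, so 43 per group. Allowing for 20% loss, 44/0.8 = 55. The figure reproduces. No effect size or power is given for Hypothesis 2.

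**2. What a test needs, against what is written.**

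| Needed | In the SAP |
|---|---|
| Psychosocial measure named in the model | Not named; open lists only |
| Effect of arm on mediator | Not stated |
| Effect of mediator on outcome, given arm | Not stated |
| Indirect effect and its interval | Not stated |
| Or: arm-by-profile interaction | Not stated |
| Or: contrast of arm effects between strata | Not stated; no cut-points; resilience not listed |

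The Hypothesis 1 section does not fill the gap: its MANCOVA covariate is FrSBe.

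**3. Effect of adjusting for a mediator.** In linear models the total effect equals c' + a×b, where a is the arm effect on the mediator, b the mediator effect on the outcome given arm, and c' the direct effect. A model that conditions on the post-randomisation mediator estimates c'. With illustrative paths a = 0.5 and b = 0.5, it drops 0.5 × 0.5 = 0.25 SD from the reported treatment effect and reports no estimate of that 0.25.

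**4. Power of a proper test.** Assumptions, not in the documents: 88 evaluable, 44 per arm, a single follow-up outcome in residual SD units.

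- *Dichotomised moderator, even split (22 per arm per stratum).* SE = sqrt(4/22) = 0.426. For a 0.71 SD interaction the noncentrality is 0.71/0.426 = 1.67 on 84 df: power 38% at 0.05 and 27% at 0.025. At 0.05, 80% power needs about 1.21 SD.
- *Continuous baseline moderator.* Approximate SE = 2/sqrt(88) = 0.213. The normal formula gives (1.960 + 0.842) × 0.213 = 0.60 SD per SD of score at 0.05, and (2.241 + 0.842) × 0.213 = 0.66 at 0.025. Simulation, which allows for t critical values and sampling variation in the score, gives about 0.63 and 0.69.
- *Mediation by joint significance at 0.05, no covariates.* Simulated power is roughly 22% for paths 0.3/0.3, 64% for 0.5/0.5 and 90% for 0.71/0.5.

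The 0.025 level is the Overview's Bonferroni rule applied to two measures (PCL and BSI-18).

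**The case against.** The best defence is that the lists are open. Overall Study Design describes Hypothesis 2 as relationships among neurological, psychological, behavioural and social variables measured repeatedly, and the Overview lists PTSD, emotional status and resilience among data collected at all three visits. The psychosocial measures could therefore be among the repeatedly measured covariates or the variables added later, and the growth model is meant to relate change to pre-existing differences between participants. This stands to the following extent: a reader might infer that the psychosocial terms are absent from the models, and the documents do not show that. They show that the terms are unnamed, that the only stated covariate role is confounder control, and that no test is attached to them.

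The stratification could also be read as placing a stratum factor in an ANOVA, where an interaction would be available. That is possible, but no such term is stated, and it would test moderation rather than the stated mediation.

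A reader might further infer that the plan will claim moderation when one stratum is significant and the other is not. The Overview gives no such rule and no number of strata. As a general hazard only: with 22 per arm per stratum and the same true 0.5 SD effect in both, power per stratum is 36.7%, so exactly one is significant in 2 × 0.367 × 0.633 = 46% of trials. That is a reason to avoid the practice, not a description of this plan.

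The SAP's opening verb for Hypothesis 2 suggests exploratory intent. That would soften the consequence, but Overall Study Design says that the hypothesis will be tested, and even an exploratory analysis must contain the variable of interest.

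**Conclusion.** The concern holds as a failure to specify the test. The hypothesis says mediation; no indirect effect, arm-to-mediator path, arm-by-profile interaction or between-stratum contrast is given. Followed as written, the analyses do not answer Hypothesis 2. This conclusion rests on the text and not on any assumed effect size; the power figures are illustrative. The primary CRIS comparison and its sample size are unaffected, so this should be corrected but does not threaten the main result.

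A separate point carries lower confidence. Table 2 shows no everyday-task test, although Hypothesis 2 uses one as its response measure, and resilience appears only in a domain label covering BSI-18 and PCL. It would be tempting to conclude that neither is measured. Table 2 refers to Appendix 1 for detail, and that appendix was not available for this review, so the documents do not support that conclusion.

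**What to change.** 1. **Mediation, as the hypothesis states.** Use post-intervention PCL and post-intervention BSI-18 as mediators, each in its own model adjusted for the baseline mediator and baseline outcome, with the 3-month follow-up value as outcome. Report indirect and direct effects with confidence intervals, and state the assumption of no unmeasured mediator-outcome confounding.
2. **If effect modification is meant, say so.** Reword the hypothesis and fit arm-by-visit-by-continuous-baseline PCL and BSI-18 terms, rather than separate tests within strata.
3. **Protect the total effect.** Do not adjust for post-randomisation PCL or BSI-18 in any model that reports it.
4. **Close the open choices.** Name one Hypothesis 2 outcome, label the analysis exploratory, and either apply the Overview's Bonferroni rule across the two measures or state that none is applied.
5. **Separately,** check Table 2 against Appendix 1 for the everyday-task and resilience instruments, and reconcile the hypothesis wording if none is scheduled.

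The cost is wording in the SAP and the hypothesis; the measures and visits are already in the plan. The downside is a narrower, openly exploratory hypothesis with the limited power shown above. Its stated outcome would change if no everyday-task measure is scheduled.

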## RANDOMIZATION OF THE COMPASS PARTICIPANTS

Randomization of the study participants will occur after all the baseline data are collected. The mTBI diagnosis including operational definition of executive dysfunction will be determined by the study Co-PI, [name], Director of the TBI Program at the DC VAMC with the participation of the DC VAMC neuropsychologist as part of the routine evaluation of Veterans referred with suspected TBI. Staff performing all outcome assessments will be blinded to group assignment throughout the study, and participants will be asked at each assessment not to reveal their group assignment to data collectors.

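### The Hypothesis 2 mixed models adjust for covariates measured after randomization and are also meant to yield treatment effects, so their arm coefficient is not the total effect of COMPASS

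*Combined protocol and SAP*

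**What the plan says.** The Hypothesis 2 section of the Statistical Analysis Plan states the adjustment twice, once in its opening paragraph and again as the first bullet: "Linear mixed models (LMM) will be used to control for confounding effects of other repeatedly measured covariates". It does not name the covariates or limit them to baseline values. On scope it says "SAS PROC MIXED will be used to estimate a LMM for each outcome of interest". Later in the same bullet list comes "We will add time-invariant variables such as treatment group into the multi-level model (MEME)", with executive dysfunction and real-life task performance as the outcomes. The stated purpose is to "relate the observed changes to pre-existing differences between TBI subjects, and determine treatment effects".

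Four other places bear on this:

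- **Randomization section:** "Randomization of the study participants will occur after all the baseline data are collected".
- **Statistical Analysis Plan, Overview:** "we plan to collect three major types of data assessed at times 1-3". The list covers PTSD, self-efficacy, emotional status, coping, real-world tasks, resilience, life satisfaction, community integration and neuropsychological measures.
- **Study Hypothesis 2:** "Individual psychosocial profile (emotional status, resilience, and level of post-traumatic stress disorder, PTSD) will mediate the responsiveness to the COMPASS" intervention.
- **Overview, on stratification:** the candidate factors include "severity of conditions secondary to TBI (PTSD, level of functioning, emotional status), or degree of societal participation". No time point is given.

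**The concern.** A confounder must be a common cause, or a proxy for one, of treatment and outcome. In a randomized comparison nothing measured after allocation can be that. A post-randomization value can, however, be changed by the treatment. Adjusting for it takes out whatever part of the effect runs through it. If covariate and outcome also share unmeasured causes, adjustment creates an association between arm and outcome that randomization had ruled out.

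The plan labels the step as confounding control and defines no direct or indirect effect. A reader of the results would therefore take the arm coefficient as the effect of COMPASS on executive dysfunction or task performance, when it estimates something else.

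**Working it through.** **1. Timing.** Each repeated covariate has three values. The time-1 value precedes randomization and the time-2 and time-3 values follow it. A time-1 value can adjust for chance imbalance. The later two have no systematic confounding to remove.

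**2. Which covariates could be meant.** The section names none, so I set the available measures beside the roles the documents give them. Study Hypothesis 2 makes emotional status, resilience and PTSD mediators. The Study Summary gives better self-efficacy as a way the program works. The Overview counts pre-to-post change in all three data types as the primary outcome. By the plan's own account, hardly any repeated measure can be assumed untouched by treatment.

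**3. The plan's power figure.** Inputs from the power section: standardized effect 0.71, SD 7, two-sided alpha 0.05, power 90%.

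- Normal formula: n = 2(1.960 + 1.282)² / 0.71² = 21.02 / 0.504 = 41.7, so 42 per arm. The noncentral t gives 43; the plan states 44.
- Power at 44 per arm is 90.9% (noncentral t).
- 44 / 0.80 = 55 per arm, 110 in total, as stated.
- 0.71 × 7 = 4.97 points.

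The figure reproduces. It is for an unadjusted comparison, that is, for the total effect.

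**4. What adjustment does (illustration).** Scale the outcome change and the covariate change to a within-arm SD of 1. Let D be the total effect, a the arm's shift of the covariate, and r the within-arm correlation.

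- Adjusted arm coefficient = D − r·a
- Its variance = (2/n)(1 − r²)(1 + a²/4)

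Example: a = 0.5, r = 0.5, n = 44. The coefficient is 0.71 − 0.25 = 0.46. The standard error is √(0.04545 × 0.75 × 1.0625) = 0.190, and the ratio is 2.42.

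The documents give neither a nor r, nor any effect or SD for executive dysfunction or task performance. So a and r are assumed, and D = 0.71 and n = 44 are borrowed from the CRIS calculation. Simulation used 3,000 trials per row.

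| a | r | D − r·a | simulated coefficient | simulated power |
|---|---|---|---|---|
| 0 | 0.3 | 0.71 | 0.72 | 94% |
| 0 | 0.5 | 0.71 | 0.71 | 97% |
| 0.3 | 0.3 | 0.62 | 0.62 | 84% |
| 0.5 | 0.3 | 0.56 | 0.56 | 76% |
| 0.5 | 0.5 | 0.46 | 0.46 | 67% |
| 0.7 | 0.5 | 0.36 | 0.36 | 45% |

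**5. Direction.** The sign of r·a decides it. With a = 0.5 and r = −0.3 the coefficient rises to 0.71 + 0.15 = 0.86.

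Bias can also appear when there is no effect at all. Take D = 0, a = 0.5, and a correlation of 0.4 due wholly to a shared unmeasured cause. The formula gives 0 − 0.20 = −0.20. Simulation gave −0.20 with 16% rejections, against 0.00 and 4.7% without adjustment. Nothing is mediated in that scenario, so the whole −0.20 comes from conditioning on the covariate.

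**The case against.** The strongest reply is about scope. All the quoted model text serves Hypothesis 2, under a heading about mediation. Whether Veterans benefit is Hypothesis 1. That is tested by ANOVA of pre-to-post change, repeated-measures ANOVA, a MANCOVA with FrSBe, and a mixed model with baseline values as covariate; the powered test is a t-test on CRIS change. A reader might infer that the trial's main comparison is compromised. The documents do not support that, because neither the t-test nor the ANOVA of change names a post-randomization covariate. Two openings remain in Hypothesis 1: its mixed model also controls for possible confounders that are not named, and its MANCOVA does not say when FrSBe is measured.

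Second, the Hypothesis 2 bullets can be read apart. The covariate-adjusted mixed model is one bullet. The next two describe a model of the repeated measures alone, to which time-invariant predictors such as arm are then added, and the words on treatment effects attach to that model. On this reading the arm effect carries no time-varying adjustment. The text permits it but does not say so, and it still leaves a mixed model with repeated covariates for every outcome of interest.

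Third, it is tempting to say that the plan adjusts for PTSD, emotional status and self-efficacy. It does not say this; step 2 is an inference, though a strong one.

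Fourth, conditioning on a mediator is legitimate when a direct effect is the target. That stands. The fault is calling it confounding control and defining no such target.

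Finally, on stratification, nothing says participation would stratify its own analysis. That is an ambiguity of timing and no more.

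**Conclusion.** The point holds for the Hypothesis 2 models. As written, they combine adjustment for post-randomization covariates with a claim to determine treatment effects, and an arm coefficient obtained that way is not the total effect.

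The size cannot be derived from the documents. It depends on whether COMPASS moves the covariate, on how strongly covariate and outcome are related, and on whether they share unmeasured causes. Under the assumed positive shifts and correlations, a standardized 0.71 falls to between 0.62 and 0.36. With no shift nothing is lost, and with opposite signs the coefficient is inflated. It would be too strong to say that the bias equals the mediated share or always shrinks the effect. The power figures illustrate a mechanism and are not estimates for the primary CRIS test, which keeps its 90.9% at 44 per arm on the plan's own inputs.

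**What to change.** Change the wording in three places:

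1. **Hypothesis 2 section.** In every model from which an arm effect is reported, restrict covariates to named, prespecified time-1 values. Put post-baseline psychosocial values in a separate analysis labelled as the Hypothesis 2 mediation analysis. Define its direct and indirect effects, name the mediators and their time points, and state the assumption about unmeasured common causes of mediator and outcome.
2. **Hypothesis 1 section.** Name the possible confounders in the mixed model and take them at time 1. State that the MANCOVA uses time-1 FrSBe.
3. **Overview.** Define all strata from time-1 values.

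No new data or visits are needed, and the powered test is unchanged. The cost is that slightly less residual variance is explained. The rows with a = 0 show the most that is given up in this illustration (94% to 97% power, against 90.9% unadjusted), and that gain is free of bias only if treatment leaves the covariate alone.
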